7.4. Injection Site Assessments

Injection site assessments will be performed immediately and 1 hour after administration of each dose of study drug (Table 1). The injection site(s) will be assessed for erythema, induration, ecchymosis, and pain, and severity will be graded according to the following criteria:

- Injection-site erythema, injection-site induration, and injection-site ecchymosis will be graded according to measurements: absent, 5 mm to ≤ 50 mm (mild), >50 to ≤ 100 mm (moderate), and >100 mm (severe).

Injection-site pain will be measured as summarized in Table 3.

If a patient has severe injection site induration, erythema, and/or ecchymosis and/or grade 3 (severe) or grade 4 (worst possible) injection site pain at 1 hour after completion of study drug administration, the patient will be reassessed at 3 hours after study drug administration and hourly thereafter until the reaction/pain is of moderate or less severity.

Table 3: Severity of Pain Scale for Injection Site Assessments

Grade	Assessments
0	No pain
1	Mild
2	Moderate
3	Severe
4	Worst possible

Number (%) of patients having injections and their post injection assessments for erythema, induration, ecchymosis, and pain of each grade will be summarized by visits and timepoints for each treatment group. The patient will be counted once if he/she has different grade reaction/pain at different injection sites after the 1st dose, the highest grade will be counted.

7.5. Deaths

If any patient dies during the study all relevant information will be discussed in the patient's narratives included in CSR.

7.6. Clinical Laboratory Tests

Clinical laboratory tests (serum chemistry, hematology, coagulation, and urinalysis) will be performed at the time points detailed in [Table 1](#) using the central laboratory. Specific laboratory tests to be performed are listed below in [Table 4](#).

Table 4: Clinical Laboratory Test

Serum chemistry	Hematology	Coagulation	Urinalysis

 • calcium • phosphorus • sodium • potassium • chloride • carbon dioxide • magnesium • glucose • blood urea nitrogen • creatinine • ALT • AST • total bilirubin • direct bilirubin • indirect bilirubin (calculated) • lactate dehydrogenase • GGT • ALP • albumin • creatine phosphokinase • total protein 	
 • hemoglobin • hematocrit • RBC count • RBC indices 
 - mean corpuscular volume - mean corpuscular hemoglobin concentration - RBC distribution width • platelet count • WBC count and differential count (absolute values and percentages) 
 - neutrophils - lymphocytes - eosinophils - monocytes - basophils 	
 • prothrombin time • partial thromboplastin time • INR 	
 • color and appearance • specific gravity • pH • blood (hemoglobin) • glucose • albumin • protein • ketones • leukocyte esterase • nitrite • direct bilirubin • microscopic 
 - bacteria - RBCs - WBCs - casts - crystals

ALP=alkaline phosphatase; ALT=alanine aminotransferase; AST=aspartate aminotransferase; GGT=gamma-glutamyl transpeptidase; INR=international normalized ratio; RBC=red blood cell; WBC=white blood cell.

Laboratory tests results and changes from baseline for chemistry, hematology, urinalysis, and coagulation laboratory tests will be summarized by visits for each treatment group using descriptive statistics. Shifts (below, within, and above the normal range) from baseline to each visit and endpoint will be summarized using patient counts. Listings of all individual patients’ laboratory test results will be presented.

The incidence of potentially clinically significant abnormal results will be summarized using descriptive statistics with the criteria specified in [Table 5](#). The potentially clinically significant abnormal laboratory values will include all postbaseline values (including scheduled, unscheduled, and early termination visits) for the summaries. Listings of patients who have potentially clinically significant abnormal laboratory data will be presented.

Table 5: Criteria for Potentially Clinically Significant Laboratory Values

Test	Criterion value	
Serum chemistry		
ALT	≥3x ULN	
AST	≥3x ULN	
ALP	≥3x ULN	
GGT	≥3x ULN	
LDH	≥3x ULN	
BUN	≥10.71 mmol/L	
Creatinine	≥177 μmol/L	
Uric acid	Men	≥625 μmol/L
	Women	≥506 μmol/L
Bilirubin (total)	≥34.2 μmol/L	
Hematology		
Hematocrit	Men	<0.37 L/L
	Women	<0.32 L/L
Hemoglobin	Men	≤115 g/L
	Women	≤95 g/L
WBC counts		≤3 x 10 ⁹ /L ≥20 x 10 ⁹ /L
Eosinophils		≥10%
ANC		≤1 x 10 ⁹ /L
Platelet counts		≤75 x 10 ⁹ /L ≥700 x 10 ⁹ /L
Urinalysis		
HGB		≥2 unit increase from baseline
Glucose		≥2 unit increase from baseline
Ketones		≥2 unit increase from baseline
Total protein		≥2 unit increase from baseline

ULN=upper limit of normal range.

ALP=alkaline phosphatase; ALT=alanine aminotransferase; ANC=absolute neutrophil count AST=aspartate aminotransferase; BUN=blood urea nitrogen; GGT=gamma- glutamyl transpeptidase; HGB=hemoglobin; INR=international normalized ratio; LDH=lactate dehydrogenase; RBC=red blood cell; ULN=upper limit of normal range; WBC=white blood cell

Serum beta-human chorionic gonadotropin (β-HCG) tests will be performed for all women of childbearing potential at screening (visit 1), and urine β-HCG tests will be performed for women of childbearing potential at visits 2 through 5. Positive pregnancy test results will be listed.

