7.3. Adverse Events

All adverse events will be coded using the MedDRA version 18.1.

For adverse event recording, the study period is defined for each patient as the time period from signature of the informed consent form through completion of visit 5 or the early withdrawal visit for patients who withdraw from the study for any reason.

Adverse events will be collected at each visit via adverse event inquiry.

The following are considered protocol-defined adverse events to be sent to the sponsor's Global Patient Safety and Pharmacovigilance Department for evaluation: ophthalmic adverse events of at least moderate severity, events of possible drug-induced liver injury (aspartate aminotransferase [AST] or alanine aminotransferase [ALT] $\geq 3 \times$ the upper limit of the normal

range [ULN], total bilirubin $\geq 2 \times$ the ULN or international normalized ratio [INR] >1.5), Hy's Law events, or events of suspected anaphylaxis and severe hypersensitivity reactions. Severe hypersensitivity reactions will be monitored using the diagnostic criteria for anaphylaxis as outlined by the 2006 Joint National Institute of Allergy and Infectious Disease/Food Allergy and Anaphylaxis Network Second Symposium on Anaphylaxis (Sampson et al 2006). In the event of suspected anaphylaxis, vital signs, including oxygen saturation and respiration rate, will be measured.

Summaries by treatment group will be presented for treatment emergent adverse events (overall and by severity), treatment emergent adverse events determined by the investigator to be treatment-related adverse events (overall and by severity), serious adverse events, protocol-defined adverse events, adverse events causing discontinuation from the study, non-serious treatment emergent adverse events and prior to treatment adverse events. Additionally the injection site reactions recorded as adverse events will be summarized by treatment group separately.

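### Table 5 has no INR >1.5 row and no within-patient combined liver count, so by-arm counts of these two Section 7.3 patterns depend on adverse-event recording

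*SAP*

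**What the plan says.** Section 7.3 lists the protocol-defined adverse events that go to the sponsor's pharmacovigilance department. Among them is possible drug-induced liver injury, with AST or ALT ≥3x ULN, total bilirubin ≥2x ULN or INR >1.5 as thresholds. The end of that definition, and the next item on the list, read "the ULN or international normalized ratio [INR] >1.5), Hy's Law events". The section gives no laboratory rule for Hy's Law. These events reach the report through the adverse-event summaries by treatment group, which include "serious adverse events, protocol-defined adverse events, adverse events causing discontinuation from the study", and through a listing. On the source of the data it says "Adverse events will be collected at each visit via adverse event inquiry".

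Section 7.6 handles the laboratory data. Table 4 puts ALT, AST, total bilirubin and INR on the central laboratory panel, and Table 1 schedules chemistry and coagulation at every visit. For flagged values, "The incidence of potentially clinically significant abnormal results will be summarized using descriptive statistics with the criteria specified in" Table 5, using every postbaseline value, including those from unscheduled and early termination visits. Table 5 has single-test rows for ALT, AST, ALP, GGT and LDH (each ≥3x ULN) and for total bilirubin (≥34.2 µmol/L). It has blocks for chemistry, hematology and urinalysis but none for coagulation.

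Section 7.6 also provides by-visit descriptive statistics that name coagulation, shift counts against the normal range, a listing of all results, and a listing of patients with flagged values.

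**The concern.** Section 7.3 states numerical liver thresholds, and the tests they need are all measured centrally. The laboratory section does not carry all of these thresholds into a count. Two items are left out: INR >1.5, and the joint occurrence in one patient of a raised aminotransferase with raised bilirubin or INR. For these two, the by-arm number in the report is whatever was recorded as a protocol-defined adverse event.

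Safety and tolerability are a primary objective (Section 1.1). A Hy's Law assessment depends on whether the same patient had both abnormalities, and separate counts per test cannot answer that. If recording differs between sites, the joint pattern could be under-counted although the data to count it are in the database.

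**Working it through.** There is no sample size or power figure to reproduce. The check sets each Section 7.3 component against Section 7.6.

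| Component in Section 7.3 | By-arm count from laboratory data in Section 7.6? | Other laboratory output |
|---|---|---|
| AST or ALT ≥3x ULN | Yes, same cut in Table 5 | By-visit statistics, shifts, listings |
| Total bilirubin ≥2x ULN | Yes, but at a fixed 34.2 µmol/L | By-visit statistics, shifts, listings |
| INR >1.5 | No row | By-visit statistics, shifts against the normal range, listing of all results |
| Hy's Law or combined pattern | No rule | Only by reading the patient listings |

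**Bilirubin.** The two criteria coincide when 2 × ULN = 34.2, that is, at ULN = 34.2 / 2 = 17.1 µmol/L. The SAP gives no ULN, so a range has to be assumed:

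- ULN 17: 2 × 17 = 34 µmol/L, just below the Table 5 cut.
- ULN 20.5: 2 × 20.5 = 41.0 µmol/L. Values from 34.2 up to 41.0 are flagged by Table 5 but do not meet Section 7.3.
- ULN 21: 2 × 21 = 42 µmol/L, with the same direction of difference.

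Over most of this range Table 5 is the more inclusive rule. The difference is one of consistency, not of missed patients.

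**Who is missed depends on how the Section 7.3 thresholds are read.** If they are alternatives, a patient whose only abnormality is INR >1.5 enters neither the Table 5 count nor the listing of flagged patients. A patient with isolated bilirubin ≥2x ULN but under 34.2 µmol/L would also escape, but only if the ULN is below 17.1. If the aminotransferase criterion must be met together with one of the others, every such patient is already in the ALT or AST row. What is lost is then only the knowledge that the second abnormality was in the same patient.

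**Why separate rows do not give the joint count.** As an illustration with assumed numbers, let one arm show 2 patients in the ALT row and 2 in the bilirubin row. The number with both can be 0, 1 or 2, and the number of distinct patients is 2 + 2 − overlap, so 4, 3 or 2. The table looks the same in all three cases.

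**Uric acid.** Table 5 sets uric acid criteria for men and women, but uric acid is not among the Table 4 tests. The planned panel gives that row no data.

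**The case against.** The strongest reply is that most of the liver information is already there. Aminotransferase, ALP, GGT and bilirubin elevations are counted from all postbaseline laboratory values. INR falls under the coagulation by-visit summaries and, read with that sentence, the shift counts. All individual results are listed, so coincident elevations can be found. The two bilirubin rules serve different purposes, one for expedited evaluation and one for tabulation, and need not be identical. How a laboratory value becomes an adverse event may be settled in the protocol, which is not at hand.

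Much of this stands, and it rules out a stronger reading. A reader might infer that any liver signal in the central laboratory data is tabulated only if a site reports it as an adverse event, or that a patient meeting the liver definition could appear in no incidence table at all. Section 7.6 does not support the first inference: the single-test rows work without any adverse-event record. The second can hold only if the thresholds are alternatives, and then mainly for isolated INR >1.5. A reader might also take the bilirubin difference as a route to missed cases, but above a ULN of 17.1 µmol/L it over-flags. Nor does the Table 5 footnote show that an INR row was dropped. It reads in part "INR=international normalized ratio; LDH=lactate dehydrogenase; RBC=red blood cell", and RBC has no row either.

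The reply does not supply the two counts. By-visit statistics dilute rare outliers, shift tables use the normal range and treat each test alone, and a listing gives no number by arm. Even if the protocol requires sites to report values over the thresholds, the count would still rest on that reporting being complete.

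**Conclusion.** The point holds in a narrow form. Two items lack a laboratory-derived by-arm count: INR >1.5, and a raised aminotransferase together with raised bilirubin or INR in the same patient. Both depend on the event being recorded as a protocol-defined adverse event. The bilirubin criteria of Section 7.3 and Table 5 agree only at a ULN of 17.1 µmol/L and should be reconciled. The uric acid row is a minor mismatch with no bearing on liver safety.

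This is a cheap improvement to the safety tabulation, not a fault in the trial's inference. No efficacy result changes, and the underlying values are summarized and listed. The number of patients affected cannot be derived from the SAP. The conclusion assumes that no other planned output, outside this document, already gives the combined count.

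**What to change.** In Section 7.6:

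- Add a by-arm count of patients with any postbaseline INR >1.5.
- Add a by-arm count of patients with (ALT or AST ≥3x ULN) and (total bilirubin ≥2x ULN or INR >1.5) on the same draw, derived from the central laboratory data. The thresholds are those of Section 7.3. Pairing should stay within one draw: scheduled treatment-period visits are about 28 days apart, so pairing neighbouring visits would join values about a month apart.
- List each patient in the combined count, with a flag for whether a protocol-defined adverse event was reported.
- Reconcile the Table 5 bilirubin criterion with Section 7.3, or state why they differ.
- Reconcile the uric acid row with Table 4.

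The cost is a few lines of text, one derived table with its listing, and the work of reconciling a few laboratory-only hits against the adverse-event data. No new sample is needed.

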4. GENERAL ISSUES FOR DATA ANALYSIS

4.1. General

Descriptive statistics for continuous variables include count (n), mean, SD, standard error (SE), median, minimum, and maximum. Descriptive statistics for categorical variables include patient counts and percentages.

Summaries of potentially clinically significant abnormal values will include all post-baseline values (including scheduled, unscheduled, and early termination visits).

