7.7. Vital Signs

Vital signs (pulse, systolic and diastolic blood pressure, body temperature, and respiratory rate) will be measured before other assessments (e.g., blood draws and administration of questionnaires) at the time points detailed in [Table 1](#).

For any abnormal vital sign finding, the measurement should be repeated as soon as possible. Any vital sign value that is judged by the investigator as a clinically significant change (worsening) from a baseline value will be considered an adverse event.

Vital signs values and changes from baseline to each visit and endpoint will be summarized using descriptive statistics. The incidence of potentially clinically significant abnormal values will be summarized for selected vital signs using descriptive statistics.

[Table 6](#) specifies the criteria for identifying vital signs as potentially clinically significant abnormal. Note that in order to be identified as potentially clinically significant abnormal, a value would need to meet both conditions below: i.e., have a value beyond the criterion value and a change of at least the magnitude specified in the change from baseline column. The potentially clinically significant abnormal vital signs values will include all post baseline values (including scheduled, unscheduled, and early termination visits) for the summaries.

Table 6: Criteria for Potentially Clinically Significant Vital Signs

Vital Sign	Criterion value	Change relative to baseline
Pulse	≥120 bpm	Increase of ≥15 bpm
	≤50 bpm	Decrease of ≥15 bpm
Systolic blood pressure	≥180 mm Hg	Increase of ≥20 mm Hg
	≤90 mm Hg	Decrease of ≥20 mm Hg
Diastolic blood pressure	≥105 mm Hg	Increase of ≥15 mm Hg
	≤50 mm Hg	Decrease of ≥15 mm Hg
Respiratory rate	<10 breaths/min	
Body temperature	≥38.3°C	Change of ≥1.1°C

bpm=beats per minute

A listing for clinically significant abnormal vital signs will be presented.

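### Table 5 counts blood values beyond a fixed limit without regard to baseline, so the chemistry and haematology incidence can mix pre-existing with new abnormalities; splitting the count by baseline status would separate them

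*SAP*

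**What the plan says.** Section 4.1 gives the general rule: "Summaries of potentially clinically significant abnormal values will include all post-baseline values", whether from scheduled, unscheduled or early termination visits. Section 7.6 repeats it for laboratory data: "The potentially clinically significant abnormal laboratory values will include all postbaseline values (including scheduled, unscheduled, and early termination visits) for the summaries". In Table 5 every chemistry and haematology criterion is a fixed limit, for example eosinophils at or above 10%, haemoglobin at or below 115 g/L in men and 95 g/L in women, or GGT at or above 3 times the upper limit of normal.

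Two neighbouring rules refer to baseline. The four urinalysis rows of Table 5 each require "≥2 unit increase from baseline". For vital signs, Section 7.7 says that "in order to be identified as potentially clinically significant abnormal, a value would need to meet both conditions below", namely to "have a value beyond the criterion value and a change of at least the magnitude specified in the change from baseline column". The exception in Table 6 is respiratory rate, which has only "<10 breaths/min".

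Section 7.6 also plans other laboratory outputs: "Laboratory tests results and changes from baseline for chemistry, hematology, urinalysis, and coagulation laboratory tests will be summarized by visits for each treatment group"; "Shifts (below, within, and above the normal range) from baseline to each visit and endpoint will be summarized using patient counts"; a listing of all results; and a listing of patients with PCS values. PCS incidence itself is summarized descriptively.

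**The concern.** The table is presented as an incidence and will be read as what happened on treatment. Under the rule as written, a patient whose eosinophils or haemoglobin were already beyond the limit before dosing enters it on the strength of a single post-baseline value that is still beyond it. The blood rows are the main place where the SAP's PCS rules make no use of baseline, although Section 2.2.4 frames the laboratory safety endpoint as change from baseline.

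What is at stake is the legibility of a safety signal. Pre-existing abnormalities add roughly the same background to every arm. When new events are rare, that background can make up much of the placebo count, pull the ratio between arms toward 1, and add chance variation to small numbers. No other planned table gives the number of newly PCS patients by arm.

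**Working it through.** **1. Is the missing count available elsewhere in the plan?**

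- The shift tables use below, within and above the normal range, not the Table 5 limits. A patient who goes from just above the upper limit of normal to 3 times that limit is recorded as above to above, so a new PCS event can be invisible there.
- The change-from-baseline summaries describe each group's distribution (mean, SD, median, range). They do not count patients crossing a limit.
- The listings would allow a manual reconstruction, but they are not a tabulation by arm.

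**2. How large could the effect be?** The SAP states no PCS rate, so there is no figure to reproduce. The inputs are:

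- Group sizes: 340 randomized per group (Section 2.3), so 680 on active drug pooled and 340 on placebo. Section 7.1 plans summaries by group and for all active drug. All patients are assumed to be in the safety population.
- New-onset PCS rate among patients not beyond the limit at baseline: assumed p1 = 2.0% on active drug and p0 = 0.5% on placebo.
- b: share of patients beyond the limit at baseline, the same in each arm through randomization. Assumed range 0 to 3%.
- s: share of those patients with at least one post-baseline value beyond the limit. Assumed 1, the same in each arm.

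Tabulated rate in an arm = b × s + (1 − b) × p.

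Risk difference = (1 − b) × (p1 − p0). The background term b × s cancels in the difference but not in the ratio.

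At b = 1%: active 0.01 + 0.99 × 0.02 = 2.980%; placebo 0.01 + 0.99 × 0.005 = 1.495%; ratio 1.99; difference 0.99 × 1.50 = 1.485 points.

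| b | Active | Placebo | Ratio | Difference (points) |
|---|---|---|---|---|
| 0% | 2.000% | 0.500% | 4.00 | 1.500 |
| 0.5% | 2.490% | 0.998% | 2.50 | 1.493 |
| 1% | 2.980% | 1.495% | 1.99 | 1.485 |
| 2% | 3.960% | 2.490% | 1.59 | 1.470 |
| 3% | 4.940% | 3.485% | 1.42 | 1.455 |

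Restricting numerator and denominator to patients not beyond the limit at baseline returns a ratio of 4.00 and a difference of 1.50 points at every b.

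**3. The same in patients, at b = 1%.** New-onset cases: 0.99 × 680 × 0.02 = 13.5 on active drug and 0.99 × 340 × 0.005 = 1.7 on placebo. Pre-existing cases: 6.8 and 3.4. About two-thirds of the placebo count (3.4 of 5.1) would be pre-existing. The binomial SD of that pre-existing placebo count is √(340 × 0.01 × 0.99) = 1.8, as large as the expected number of new placebo cases. Randomization balances the background only in expectation.

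**4. Sensitivity to the assumptions.**

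- If only half of the baseline-abnormal patients have a later value beyond the limit (s = 0.5), then at b = 1% the rates are 0.005 + 0.0198 = 2.480% and 0.005 + 0.00495 = 0.995%, and the ratio is 2.49 rather than 1.99.
- With new-onset rates of 4% versus 1% and s = 1, the ratio falls from 4.00 to 2.49 at b = 1% and 1.48 at b = 5%. The difference moves only from 3.00 to 2.97 and 2.85 points.

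**The case against.** The case against is substantial. Table 5 is complete and reproducible, and Section 7.6 applies the rule of Section 4.1 faithfully, so nothing is contradictory. Different measurements may reasonably have different rules: urinalysis uses an increase alone, vital signs a limit plus a change, and respiratory rate a limit alone. Many blood limits lie far from normal, where few patients should start. Table 6 asks for a minimum change and does not exclude patients abnormal at baseline, so a new-onset count would not copy it exactly. Baseline-referenced views exist in the change summaries, shift tables and listings, and possible drug-induced liver injury is summarized separately as a protocol-defined adverse event (Section 7.3). Keeping every patient in the main safety table is a defensible, conservative choice.

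Most of this stands. It rules out calling the rule an error, and it argues against removing baseline-abnormal patients from the main table, where further worsening in them should stay visible. It does not supply a new-onset PCS count by arm.

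A reader might infer that drug-related laboratory signals are in fact diluted in this trial. The SAP does not support that: it gives no baseline prevalence, and any laboratory eligibility limits would be in the protocol, which was not available for this review. A reader might also infer a loss of statistical power. No between-arm test of PCS incidence is planned, so no planned test can lose any.

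**Conclusion.** The point holds as a minor, conditional one. The chemistry and haematology rows carry no baseline condition, so any patient beyond a limit both before and after the first dose is counted as a post-baseline PCS case, and no planned table separates such patients from new cases.

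The size depends wholly on the share of patients beyond a limit at baseline. It is zero if there are none. It is most plausible for limits such as eosinophils at or above 10% or low haemoglobin or haematocrit, and least so for the extreme limits. Under the assumed 2.0% versus 0.5% with full persistence, the ratio falls from 4.0 to about 2.0 at 1% and 1.4 at 3%, while the risk difference loses at most 0.045 points. Efficacy conclusions, the testing sequence and the sample size are untouched. What is gained is a clearer reading of rare laboratory events.

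**What to change.** In Section 7.6, keep the all-patient PCS count and add a split by baseline status for each chemistry and haematology criterion:

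- new-onset PCS, with numerator and denominator restricted to patients who do not meet the criterion at baseline and have at least one post-baseline value;
- a separate row for patients who already met the criterion at baseline.

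Keep all values in the listing. Baseline is already defined in Section 4.2 as the last value before the first dose, and laboratory tests are scheduled at screening and visit 2, so no new data are needed. The cost is one SAP sentence, a baseline flag per criterion and extra table rows. Because the all-patient count stays, no patient leaves the display.
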